### **7.9. Analysis of Secondary Effectiveness Endpoints**

Secondary continuous effectiveness endpoints will be summarized by treatment group over time and as changes over time with descriptive statistics including means, standard deviations,

median, minimum and maximum values. Secondary categorical effectiveness endpoints will be summarized by treatment group over time using counts and percentages. Descriptive effect size measures such as mean differences and differences in percentages responding will be provided with 95% confidence intervals or 95% credible intervals as an aid in evaluating the likely ranges of true treatment group differences.

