**Other Methods:**

An alternative composite endpoint will be evaluated that replaces improvements in ODI with improvements in a walking treadmill test. Secondary continuous effectiveness endpoints will be summarized by treatment group over time and as changes over time with descriptive statistics including means, standard deviations, median, minimum and maximum values. Standardized effect sizes (i.e., standardized mean differences) will be computed to facilitate comparisons across measures. Secondary categorical

	
effectiveness endpoints will be summarized by treatment group over time using counts and percentages.
 
Adverse event rates will be summarized by type of AE and for specific AE per patient using counts and percentages; and by event, summarizing event counts by visit interval over time. Device and procedure related events will be summarized by severity. Events listings will be provided that include details such as relatedness, severity, onset and resolution status will be provided for all events and for relevant subsets of events such as serious events and related events.

--	---

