### 3.3. Secondary Endpoints

- ODI change compared to baseline at 24 and 60 months as a continuous variables and in terms of achieving at least a 15 point improvement.
- Change in Visual Analog Scale (VAS) for low back pain (on the 100 mm scale) after 24 and 60 months compared to baseline as a continuous variables and in terms of achieving a 20 point improvement.
- Change in right and left leg pain using a Visual Analog Scale (VAS) 100 mm scale after 24 and 60 months compared to baseline as a continuous variable and in terms of achieving a 20 point improvement. A separate analysis will be performed to compare VAS scores for the “worst” legs.
- Change of Zurich Claudication Questionnaire (ZCQ) after 24 and 60 months compared to baseline:
  - Symptom severity (range 1-5)
  - Physical function (range 1-4)
  - Patient satisfaction (range 1-4, no baseline).
  - ZCQ Overall Success ( $\geq 2$  of 3 of the following)
    - Improvement in symptom severity  $\geq 0.5$
    - Improvement in physical function  $\geq 0.5$
    - Satisfied or somewhat satisfied as defined by a score of  $\leq 2.5$  points on the patient satisfaction domain.
  - ZCQ Overall Success components
- Maintenance or improvement in EQ-5D compared to baseline
- Change from baseline to Month 24 and Month 60 in maximum walking time from treadmill test as a continuous variable and in terms of achieving at least an 8 minute improvement or maximum time of 15 minutes.
- Change from baseline to Month 24 and Month 60 in time to symptoms from treadmill test as a continuous variable and in terms of achieving at least an 8 minute improvement or maximum time of 15 minutes.
- Neurological status (no new or worsening, persistent neurological deficit)
- Radiography Endpoints
  - Assessment of significant migration of the implant or the complete expulsion (significant is defined  $> 5$  mm).
  - Assessment of spinous process fracture.
  - Assessment of maintenance of foraminal height
  - Assessment of adjacent level disease determined by independent radiographic review
- Correlation of foraminal height changes to improvement of walking distance on a treadmill (after 24 and 60 months compared to baseline).

 Pratt RK et al., The Reliability of the Shuttle Walking Test, the Swiss Spinal Stenosis Questionnaire, the Oxford Spinal Stenosis Score and the Oswestry Disability Index in the Assessment of Patients with Lumbar Spinal Stenosis. Spine Vol. 27 (1) pp. 84-91.

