## 7. Statistical Analysis

### 7.1. Accounting for Non-Randomized Treatment Group Comparisons

This study design includes concurrently enrolled, but non-randomized investigational and control arms. Covariate balance will be achieved using sub classification based on propensity score (PS) quintiles. The PS subclasses will be determined by an outcomes-blinded statistician soon after prospective enrollment is completed and before most if not all patients are evaluable for the two-year effectiveness endpoint. The process of assigning patients to subclasses will be submitted to FDA for review and acceptance prior to unblinding of the PS statistician. Selection into a PS subclass is the observational study equivalent to randomization. Subclasses will be determined using methods summarized below to ensure that within subclass, groups are well balanced for a rich set of clinically relevant baseline covariates. Analyses will proceed as if patients were

randomized to treatment group within subclass and effectiveness outcomes will be compared between groups using methods that account for PS subclass. There is a compelling case to be made that informative prior Bayesian designs are especially appropriate for post approval studies (PAS) since recent rigorous objective data is available. To make use of this prior information, a Bayesian design with informative priors has been specified for each Objective. For these Objectives, patient-level data from the IDE study are used to formulate the PAS prior distributions.

To make use of the beta-binomial updating from prior to posterior it is necessary to have counts of the numbers of successes and failures observed among the prospectively enrolled patients for both groups. These counts are added to prior beta distribution parameters that reflect (what amounts to) the prior numbers of success and failures. Combined, these sums of successes and failures determine the Bayesian posterior distribution. The simplicity of this approach stems from the mathematical convenience of conjugate priors which have, in addition to computational convenience, the practical advantage of being interpreted as additional data (Gelman, 2014). However, the numbers of successes and failures observed from each group to be used to update the prior distribution must account for the propensity subclass design.

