## 7.15. Risk Factor Analysis

Logistic regression analysis may be used to assess potential factors associated with success or failure of the investigational device including age, gender, BMI, and baseline ODI.

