## 7.17. Design and Conduct of Observational Study

### 7.17.1. Propensity Score Analysis

The study design includes concurrently enrolled, but non-randomized investigational and control arms. Subjects groups will also be comparable with regard to timing of treatment owing to concurrent enrollment. Propensity score subclassification (Rosenbaum and Rubin, 1983) will be used to addresses potential selection bias inherent in non-randomized comparisons. The PS model will be evaluated according to rigorous criteria (Imbens and Rubin 2015) using a published heuristic (Maislin and Rubin 2010). Applications of this heuristic have been recently been published (e.g., Keenan, Maislin, et al 2014; Arnardottir, Lim, Keenan, Maislin et al 2014; and Pak, Keenan, Jackson, Grandner, Maislin et al 2014). The heuristic is designed to identify 5 sub classes in which the groups to be compared share the same multivariate distribution of a comprehensive set of baseline variables. Within each sub class, patients are therefore equally likely to have received the investigational device or control. The primary treatment comparison will be based on PS-quintile stratified analyses.

The propensity score is the observational study analogue of complete randomization in randomized experiments in the sense that its use is not intended to increase precision but only to

 Hosmer DW and Lemeshow S. Applied Logistic Regression. New York: John Wiley & Sons, 1989.

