### 7.17.2. Variables to be Included in PS Model

The following tables list information to be used to construct variable for the PS modeling. Variables include demographic factors, baseline disease severity factors, radiographic factors, and site and surgeon factors. The final formulation of variables derived from the following factors will be defined by the statistician responsible for conducting the PS modeling and without regard to outcome data.

Variable	Location of Variable in CRF
Age	CRF Form 1
Gender	CRF Form 2
Race	CRF Form 2
Ethnicity	CRF Form 2
BMI	CRF Form 2
Duration of symptoms	CRF Form 2
Pain management	CRF Form 2
Prior treatment	CRF Form 2
Current or former smoker	CRF Form 2
Work Status	CRF Form 2
Cross-sectional area of spinal canal	Core Lab
Foraminal area	Core Lab
Diagnoses	CRF Form 4
Ortho/neuro surgeon	CRF Form 4
VAS-leg (max)	CRF Form 7
VAS-back	CRF Form 7
ODI	CRF Form 8
ZCQ physical function	CRF Form 9

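### Section 7.9 compares secondary continuous outcomes without the baseline value as a covariate and does not say whether PS subclass is applied

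*Combined protocol and SAP*

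**What the plan says.** Section 7.9 is the whole analysis plan for the secondary continuous endpoints: "Secondary continuous effectiveness endpoints will be summarized by treatment group over time and as changes over time with descriptive statistics". For the group comparison it adds: "Descriptive effect size measures such as mean differences and differences in percentages responding will be provided with 95% confidence intervals or 95% credible intervals". The stated purpose is to help judge how large the true group differences may be. The synopsis (Other Methods) adds: "Standardized effect sizes (i.e., standardized mean differences) will be computed to facilitate comparisons across measures". Neither place names a model or a covariate.

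Section 3.3 defines most of these endpoints as changes, for example "Change from baseline to Month 24 and Month 60 in maximum walking time from treadmill test as a continuous variable". The patient's own baseline is therefore used, by subtraction.

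Three other sections bear on the point:

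- Section 7.1 sets the general rule that "effectiveness outcomes will be compared between groups using methods that account for PS subclass". Section 7.9 neither repeats it nor says how it applies to a mean difference.
- Section 7.17.1 says of the propensity score that "its use is not intended to increase precision".
- Section 7.17.2 describes the PS inputs: "Variables include demographic factors, baseline disease severity factors, radiographic factors, and site and surgeon factors". Its table lists ODI, VAS back, VAS leg (max) and ZCQ physical function. It does not list treadmill times, ZCQ symptom severity or EQ-5D.

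The only regression of an outcome on baseline variables is in 7.15, an optional logistic analysis that "may be used to assess potential factors associated with success or failure of the investigational device". It is not a group comparison of secondary endpoints.

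**The concern.** A difference in mean follow-up values ignores baseline. A difference in mean changes uses it, but assumes that each extra point at baseline carries one extra point at follow-up. When the true slope is below 1, the change score carries avoidable baseline noise, and any baseline difference between the arms shifts the estimate.

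The arms are not randomized, and each site enrolls only one arm (4.6, 7.16), so baseline differences could be systematic. Five PS subclasses reduce such differences but need not remove them within a subclass. A measure missing from the PS list is balanced only so far as it correlates with the listed ones.

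Treadmill time shows this most clearly. The test stops at 15 minutes, so a patient who walks 10 minutes at baseline can gain at most 5. Section 7.8 recognizes this in the responder rule, with a separate criterion for baselines above 7 minutes. The continuous change has no such allowance.

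At stake are the width and interpretability of the intervals offered as the plausible range of true differences. No hypothesis test is affected.

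**Working it through.** **Inputs.** Section 7.9 gives no precision figure to reproduce. Section 4.2 gives 150 patients per group. The documents give no SD for these measures and no baseline to follow-up correlation, so both are assumed and varied. Let rho be that correlation and k the ratio of baseline SD to follow-up SD.

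**Formulas.** Per-patient variance, in units of the follow-up SD squared:

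- follow-up value: 1
- change score: 1 + k² − 2·rho·k, which is 2(1 − rho) when k = 1
- baseline-adjusted: 1 − rho²

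The interval-width factor, adjusted against change score, is the square root of (1 − rho²)/(1 + k² − 2·rho·k). With k = 1 this is the square root of (1 + rho)/2.

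**Equal SDs (k = 1).** Half-width is 1.96 × √(variance × 2/150), in SD units.

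| rho | half-width, change | half-width, adjusted | variance ratio | adjusted narrower by |
|---|---|---|---|---|
| 0.2 | 0.286 | 0.222 | 0.60 | 22.5% |
| 0.3 | 0.268 | 0.216 | 0.65 | 19.4% |
| 0.5 | 0.226 | 0.196 | 0.75 | 13.4% |
| 0.7 | 0.175 | 0.162 | 0.85 | 7.8% |

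Against plain follow-up values the half-width is 0.226 throughout. Adjustment then narrows it by 1 − √(1 − rho²): 2% at rho 0.2, 13% at 0.5 and 29% at 0.7.

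**Smaller baseline SD.** Entry requires ODI of at least 40% and VAS back of at least 50 mm (4.3). Baseline is cut off from below while follow-up is not, so k below 1 is plausible for these two.

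| k | rho | variance ratio | adjusted narrower by |
|---|---|---|---|
| 0.5 | 0.5 | 0.75/0.75 = 1.000 | 0% |
| 0.7 | 0.5 | 0.75/0.79 = 0.949 | 2.6% |
| 0.5 | 0.2 | 0.96/1.05 = 0.914 | 4.4% |
| 0.7 | 0.2 | 0.96/1.21 = 0.793 | 10.9% |

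The gain is zero when k = rho, because the true slope rho/k is then 1 and the change score is already the adjusted estimate.

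**Effect of a baseline difference.** With k = 1 and an illustrative gap of 0.25 SD between arms, the change-score estimate differs from the adjusted one by (rho − 1) × 0.25. That is −0.175, −0.125 and −0.075 SD at rho 0.3, 0.5 and 0.7. The follow-up-value estimate differs by rho × 0.25, which is +0.075, +0.125 and +0.175 SD. The documents do not show that a gap of this size will occur, and subclassification should reduce it for listed measures.

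**The case against.** The strongest reply has four parts.

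- **Baseline is already used.** Changes are analyzed, and four of the relevant baseline scores enter the PS model, whose subclasses 7.1 requires effectiveness comparisons to respect. This stands. A reader might infer from 7.9 that baseline is ignored altogether, and the documents do not support that. What is missing is baseline as a covariate, and a statement in 7.9 that PS subclass is applied.
- **Imbalance is not shown.** Subclasses are built and trimmed to stated criteria, balance is verified within subclass, and FDA reviews the result before unblinding (7.17.1). In a non-randomized comparison, change score and covariate adjustment are also each unbiased under different assumptions. Both points stand. A reader might infer that these estimates are biased, but the documents show only that residual imbalance, if present, would not be removed.
- **The gain may be small.** This stands for ODI and VAS back if the baseline SD is reduced. Pooling over PS subclasses would lower the figures further for the four listed measures. A reader might turn the equal-SD result at rho 0.2 to 0.5 into the equivalent of 33% to 67% more patients. The documents give no SD or correlation to support that.
- **The outputs are descriptive.** This stands too. All four objectives rest on binary composite success.

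The proposal also has limits. ZCQ satisfaction has no baseline, EQ-5D is defined as being maintained or improved, and a linear model does not fully deal with the 15-minute treadmill cap. None of this is a reason to leave the estimator unnamed.

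**Conclusion.** The point holds as a modest improvement to secondary analyses. Section 7.9 leaves baseline out as a covariate and leaves the use of PS subclass unstated. No other section supplies the covariate, and the PS is by the plan's own account not a precision device.

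The width reduction against change scores is about 8% to 23% with equal SDs and rho 0.2 to 0.7. It is about 0% to 11% with k of 0.5 to 0.7 and rho 0.2 to 0.5. All of these values are assumed. The figures are upper bounds where PS subclass already absorbs baseline variation.

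In large samples, with baselines balanced, the adjusted estimate is never less precise than the change score. The case is strongest for treadmill times and ZCQ symptom severity, which the PS list does not cover.

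**What to change.** In 7.9, state that between-group mean differences at Months 24 and 60, for continuous measures that have a baseline, come from a linear model with treatment, PS subclass and the baseline value of the same measure, and that the 95% interval comes from that model. Keep the raw summaries by visit and as changes. Leave out ZCQ satisfaction and the EQ-5D endpoint as now defined.

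This also settles whether 7.9 follows the rule in 7.1, and it fixes the estimator before outcomes are seen. The cost is a sentence or two of SAP text and standard code. The baseline values are already collected at screening (4.8.1), so no new data are needed.

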## 7.10. Follow-Up Compliance

Follow-up compliance will be determined separately by device group on the basis of theoretical due and expected due as illustrated in FDA Guidance (2004). Separate compliance estimates for composite clinical success, and for clinical indices (i.e., ODI) will be provided over time.

## 7.11. Handling of Missing Data for Primary CCS Endpoints

### 7.11.1. Bayesian Multiple Imputation

To best preserve an intent-to-treat analysis, the testing of the primary Month 60 superiority hypothesis (Objective 1) will be done on the ITT-PS selected analysis set. Those subjects who withdraw, or who are lost to follow-up (LT FU) after enrollment will be included in the analysis using a modification of Bayesian multiple imputation to accommodate the PS subclass design. This analysis will be the primary analysis, but recognizing that there is no way, statistically, to handle these subjects without possibly introducing bias, a tipping point analysis will be also be conducted. For comparison purposes, a completers analysis will also be performed. The following describes the method. A similar method will be applied to analyses for other objectives.

In general, Bayesian Multiple Imputation (MI) may be employed to impute the expected status at Month 60 for patients who have not completed follow-up and have not been identified as “terminal failures”. Terminal failures include any event which is counted as a CCS failure no matter what happens after such an event occurs such as a secondary surgical invention. The imputation algorithm uses a beta-binomial distribution to model the transition probabilities from the outcome at month  $j$  to that at month 60, separately for the treatment and control groups. Specifically, the probability of a success for a subject in treatment group  $t$ , with last follow-up  $j$  and last follow-up value  $r$  can be described using a beta distribution:

$$\Pi_{p,t,j,r} \sim \beta(1 + S_{p,t,j,r}, 1 + F_{p,t,j,r})$$

Where  $p$  = propensity score subclass = {1, 2, 3, 4, 5}

$t$  = treatment group = {coflex=S, Decompression=D}

$j$  = follow-up time = {3, 6, 12, 24, 36, 48}

$r$  = success or failure status at time  $j$  = {1=success, 0=failure}

$\Pi_{p,t,j,r}$  = Month 60 success probability for subjects in subclass  $p$ , in treatment group  $t$ , who were successes ( $r=1$ ) or failures ( $r=0$ ) at follow-up time  $j$ .

$S_{p,t,j,r}$  = Number of Month 60 successes for subjects in subclass  $p$ , in treatment group  $t$ , who were successes ( $r=1$ ) or failures ( $r=0$ ) at follow-up time  $j$ .

 Guidance for Industry and FDA Staff Clinical Data Presentations for Orthopedic Device Applications Document issued on: December 2, 2004.

$F_{p,t,j,r}$  = Number of Month 60 failures for subjects in subclass p, in treatment group t, who were successes (r=1) or failures (r=0) at follow-up time j.

Note that these transition beta distributions assume non-informative prior distributions to allow only the observed data to impact on the multiple imputations (i.e., all a and b are set to 1). Subsequently, the informative prior on the study device group is applied to determine the posterior distribution of non-inferiority.

In order to implement the Bayesian Multiple Imputation algorithm, the following steps will be used.

1. For each patient that has not completed follow-up, a value  $\pi_i$  is randomly chosen from  $\Pi_{p,t,j,r} \sim \beta(1 + S_{p,t,j,r}, 1 + F_{p,t,j,r})$  corresponding to their PS subclass, treatment group, and success-failure status at their last known follow-up; this value represents the probability that the subject is a success at 60-months.
2. Using this randomly chosen  $\pi_i$ , the patient is then assigned a success (1) or failure (0) from a random draw of the binomial distribution  $Bin(n, p)$  with  $n = 1$  and  $p = \pi_i$ .
3. Steps 1-2 are repeated for all subjects with incomplete follow-up, separately for each treatment group and propensity score subclass.
4. Using the resulting completed datasets (containing both observed and imputed values at month 60), the PS-adjusted total number of successes ( $S_t$ ) and failures ( $F_t$ ) at month 60 are calculated for each treatment group using the average of PS subclasses as described above. The probability of success for each treatment is then chosen randomly from the resulting posterior beta distributions incorporating the informative prior in the study device group and the non-informative prior for controls. The distribution of the difference in success probabilities is therefore:

$$\pi_S - \pi_D \sim \beta(82.1 + S_t, 62.1 + F_t) - \beta(1 + S_D, 1 + F_D)$$

5. Step 4 is repeated ( $n = 10,000$  times), to obtain the posterior distribution of the differences in treatment success ( $\pi_S - \pi_D$ ), and the posterior probability of non-inferiority is calculated as the proportion of times that  $\pi_S - \pi_D \geq -\delta$ .
6. To complete the multiple imputation and obtain the final posterior non-inferiority probabilities, steps 1-5 are repeated 20 times and the final posterior probability is determined as the average of the 20 multiple imputations.

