**Ho:  $CCS_{coflex+decomp.} - CCS_{decomp} \leq 0$  (not superior)**

**Ha:  $CCS_{coflex+decomp.} - CCS_{decomp} > 0$  (superior)**

An informative prior based on IDE study results for the coflex® group will be used. A non-informative will be used for decompression alone. The Bayesian posterior probability that  $(CCS_{coflex+decomp.} - CCS_{decomp}) > 0$  will be determined. **If the posterior probability is  $\geq 0.95$ , superiority will be concluded.**

**Objective 2: (2-year non-inferiority)** This objective is to compare clinical status of patients implanted with the coflex® device in conjunction with surgical decompression relative to surgical decompression alone at two years post operatively by confirming clinical non-inferiority in terms of Month 24 composite clinical success (CCS) defined similarly to the IDE study endpoint. To meet this objective, the following hypotheses will be tested:

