The following approach will be used to determine adjusted numbers of successes and failures that account for the relative contribution of each PS subclass. This approach is necessary to produce results that take advantage of the covariate balance achieved through PS sub classification. We first consider how this would be done if there was no missing data. This is the approach that will be used in sensitivity analyses involving the several completers analysis sets defined primarily across time. The section below concerning missing data shows how missing data will be incorporated in the primary determination of the Bayesian probability of superiority and non-inferiority.

To adjust for PS subclass, the average success rate over the 5 subclasses will be computed for each treatment group. This is to allow each quintile subclass to contribute equally to the estimated success rates. Consequently, the covariate balance is preserved in the final estimates of CCS probabilities. By equally weighting the PS subclasses, the results become estimates of expected values under the assumption of randomized treatment assignment within PS subclass. Under this assumption, we would expect approximately the same number of investigational and control patients within each subclass implying the equality of weights. The PS adjusted failure probability for each group will be computed as one minus the adjusted success probability.

If the crude numbers of success and failures were used to update the priors, imbalance in the numbers of investigational and control subjects within subclasses would clearly result in a biased treatment effect estimate whenever overall success rates differed among PS subclasses.

By combining the subclass success probabilities in this way, the weights given to each subclass contribution when determining the total numbers of successes and failures used to update the prior are the same for both groups.

The PS subclass adjusted success and failure probabilities will be multiplied by the total treatment group specific sample sizes (across all subclasses) to determine PS subclass adjusted numbers of successes and failures for each group. The adjusted numbers of success and failures in each group will be added to the group specific beta distribution parameters to update the prior

---

 Gelman, A. (2014). *Bayesian data analysis* (Third edition. ed.). Boca Raton: CRC Press.

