**If the posterior probability is  $\geq 0.95$  then superiority will be concluded.**

#### 7.4. Objective 2: 2-Year Non-Inferiority

Two-year non-inferiority will be evaluated by comparing clinical status of patients implanted with the coflex® device in conjunction with surgical decompression relative to surgical decompression alone at two years post operatively by confirming clinical non-inferiority in terms of Month 24 composite clinical success (CCS) defined similarly to the IDE study endpoint. To meet this objective, the following hypotheses will be tested:

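### Section 7.11.1, the algorithm for the primary Month 60 superiority test, calculates a non-inferiority probability with an undefined margin instead of the probability that the difference exceeds zero

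*Combined protocol and SAP*

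**What the plan says.** Section 7.11.1 opens with Objective 1. It says that "the testing of the primary Month 60 superiority hypothesis (Objective 1) will be done on the ITT-PS selected analysis set", names multiple imputation as the primary analysis, and adds: "A similar method will be applied to analyses for other objectives". Step 4 draws the coflex rate from a posterior built on Beta(82.1, 62.1), which 7.7.1 gives as the Month 60 prior. It draws the control rate from a posterior built on Beta(1, 1).

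The event that is then counted is a non-inferiority event, in three places:

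- Lead-in to the steps: "the informative prior on the study device group is applied to determine the posterior distribution of non-inferiority".
- Step 5: "the posterior probability of non-inferiority is calculated as the proportion of times that" π_S − π_D ≥ −δ.
- Step 6: to "obtain the final posterior non-inferiority probabilities, steps 1-5 are repeated 20 times", and the 20 results are averaged.

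The decision rule for Objective 1 stands elsewhere. Section 7.3 sets the alternative as a difference above 0 and says that if the posterior probability is at least 0.95, "then superiority will be concluded". The synopsis gives the same hypotheses and threshold ("superiority will be concluded").

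Section 7.1 says that the missing-data section shows "how missing data will be incorporated in the primary determination of the Bayesian probability of superiority and non-inferiority". It does not say which event belongs to which objective.

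**The concern.** The quantity named in steps 5 and 6 is not the one that 7.3 compares with 0.95. The two agree only if δ is 0, and the plan does not say that it is. The plan's margins belong to other comparisons: 0.10 for Objective 2, 0.1175 (or 0.10 in 7.6) for Objective 4, and 0.10 for the IDE comparison with fusion. The sign of δ also varies. Section 2 writes it as positive, while the synopsis (Objective 4) and 7.6 write it as negative, so −δ taken literally could be a positive bound.

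Step 5 therefore cannot be programmed for the primary test without a choice that the section does not make. The tipping point analysis in 7.11.2 asks whether the primary conclusion changes, so it depends on the same event. The event for a primary test should be fixed in the plan and not left to be inferred when the program is written.

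**Working it through.** The check asks which rule produced the plan's stated Objective 1 figures.

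**Inputs**

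- n = 150 per group (4.2).
- Coflex prior Beta(82.1, 62.1) (7.7.1 and step 4).
- Control prior Beta(1, 1) (step 4).
- Cut-off 0.95 (7.3).
- Coflex Month 60 rate 0.57 (7.7.1).
- Control rate 0.57 for type 1 error, 0.57 − 0.125 = 0.445 and 0.57 − 0.10 = 0.47 for power.

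**Formulas.** With x_S and x_D successes:

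- coflex posterior: Beta(82.1 + x_S, 62.1 + 150 − x_S)
- control posterior: Beta(1 + x_D, 1 + 150 − x_D)
- P(π_S − π_D > −m) = ∫ f_S(s) · F_D(s + m) ds
- pass if this is at least 0.95
- pass rate = sum over passing pairs of Bin(x_S; 150, p_S) × Bin(x_D; 150, p_D)

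All pairs were enumerated, so there is no simulation error. The posteriors are continuous, so > and ≥ give the same result. Complete data and plain binomial counts are assumed, without imputation or propensity adjustment.

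**The plan's own figures, m = 0 (the 7.3 rule)**

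| True rates, coflex / control | Stated in 7.7.1 | Control Beta(1, 1) | Control Beta(0.5, 0.5) |
|---|---|---|---|
| 0.57 / 0.57 (type 1 error) | 0.037 (SD 0.0011) | 0.036 | 0.035 |
| 0.57 / 0.445 (power) | 83% | 82.3% | 82.2% |
| 0.57 / 0.47 (power) | 65% | 64.7% | 64.6% |

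The stated figures reproduce under the greater-than-zero rule, with either non-informative control prior.

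**Illustration only: the Objective 2 margin borrowed, m = 0.10, control Beta(1, 1)**

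| True rates, coflex / control | Pass rate |
|---|---|
| 0.57 / 0.57 | 0.671 |
| 0.57 / 0.445 | 0.999 |
| 0.57 / 0.47 | above 0.99 |

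The stated figures cannot come from this margin.

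A single data set shows how far apart the two quantities are. With 85 of 150 successes in each group, P(difference > 0) = 0.517, while P(difference ≥ −0.10) = 0.981.

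A small positive δ would also matter. At 0.57 in both groups the pass rate is 0.049 at δ = 0.0065 and 0.051 at δ = 0.007. No such δ appears in the documents.

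**The case against.** The case for leaving the text alone is substantial.

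- **The rule is already fixed.** The hypotheses and the 0.95 rule for Objective 1 stand in both 7.3 and the synopsis, 7.11.1 itself calls the test one of superiority, and 7.7.1 reports only superiority power and a type 1 error at equal rates. This stands: the intent is not in doubt.
- **The algorithm already yields the right draws.** Step 5 first obtains the posterior distribution of the difference, and P(difference > 0) can be read from the same 10,000 draws. The imputation, subclass adjustment, prior and averaging over 20 imputations are untouched. This also stands, and it limits the defect to the last clause of step 5 and two labels.
- **The section is a general template.** This holds only in part. Section 7.1 does give it both uses, but the steps are written for Month 60 with the Objective 1 prior, and nothing assigns an event or margin to an objective.

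A reader might go further and infer that the primary test will be run as a non-inferiority test, with a false-positive rate near 67%. The documents do not support that. No section assigns the 0.10 margin to Objective 1, and the stated power and type 1 error rule it out. Nor do the stated operating characteristics need revision, since they already belong to the correct rule.

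**Conclusion.** The point holds as a specification error that should be fixed. For Objective 1, the lead-in and steps 5 and 6 of 7.11.1 name the wrong posterior event and depend on a δ that is not defined. Section 7.3 and the synopsis state the right rule, and the recomputed 82.3%, 64.7% and 0.036 against the stated 83%, 65% and 0.037 confirm that the design was built on it.

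No effect on the planned operating characteristics has been shown. The 0.10 and 0.007 results show only how sensitive the conclusion would be if another margin were put into step 5. The recomputation rests on 150 evaluable patients per group, independent binomial counts, and the priors in step 4. The simulation memo behind the plan's own figures is not part of the documents.

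**What to change.** In 7.11.1, write for Objective 1: *posterior probability of superiority = proportion of draws with π_S − π_D > 0; superiority is concluded if the average over the 20 imputations is at least 0.95.* Change the non-inferiority wording in the lead-in and in steps 5 and 6 to match.

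Then state the events for the other two comparisons with decompression, as explicit numbers so that the sign of δ no longer matters:

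- Objective 2: π_S − π_D > −0.10.
- Objective 3: π_S − π_D > 0.

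Both use the priors in 7.7.2 (coflex Beta(135.5, 69.5), control Beta(0.5, 0.5)) in place of those in step 4. Section 7.7.3 already carries the Objective 2 priors over to Objective 3.

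The cost is text only. The hypothesis, threshold, Month 60 prior, sample size and stated power for Objective 1 do not change.
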